For both groups, the Scrambler machine was kept behind a curtain to help preserve masking. The machine itself was turned on for all participants, though without emitting any stimulation in those receiving sham, so that the alert indicating termination of treatment would be heard by all participants regardless of treatment assignment. Because treatment effect has been shown to vary across technicians, one technician was trained in the proper delivery of Scrambler treatment and performed all interventions.

Study objectives and measures:

Our primary objective was to test the hypothesis that Scrambler therapy is an effective, acceptable, feasible and safe treatment of persistent central neuropathic pain for patients with NMOSD. To test this hypothesis, we performed a randomized single blind, sham-controlled trial testing Scrambler therapy in patients with NMOSD. The primary outcome was feasibility and acceptability. Secondary endpoints included both safety and effectiveness at the end of the 10-day treatment period. Feasibility of treatment was examined to determine whether the intervention was appropriate for this patient population, toward the effort of informing a larger, Phase III study. This was measured by assessing the following: 1) adherence to visit schedule and 2) response to the following question asked directly after completion of the 10-day treatment period: "Do you think you received treatment?" (Yes/No). Acceptability was measured by assessing response to the following question, also asked directly following the treatment course: "Would you want to continue treatment in clinic, if available?" (Yes/No).

Safety of the intervention was evaluated by comparing Adverse Events (AEs) and Serious Adverse Events (SAEs) in the treated versus sham groups. These were monitored and documented prior to initiation of each treatment daily, at termination of final treatment, and at 30- and 60-day follow-up.

Effectiveness was evaluated based on degree of improvement in pain, comparing the treatment group to sham. Prior to initiation of Scrambler therapy and at completion of treatment, patients were asked to rate their pain by the 11-point NRS score. Patients additionally reported NRS pain

scores at 30- and 60- days following therapy completion to assess sustainability of treatment effect.

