Although not powered appropriately, an exploratory objective aimed to assess the relationship between improved pain and other co-occurring symptoms. Prior to initiation of Scrambler therapy, patients were asked to complete each of the following measurement tools to determine baseline pain severity and interference, anxiety, depression, and sleep disturbance, respectively: Brief Pain Inventory (BPI), Neuro-QoL [Quality of Life in Neurological Disorders] Short Form v1.0 - Anxiety, Neuro-QoL Short Form v1.0 - Depression, and Neuro-QoL Short Form v1.0 - Sleep Disturbance. Measurement tools were accessed by participants via a secure online portal. Participants were provided with an alphanumeric code that enabled their responses to be linked to their demographic and clinical data in a confidential manner. Questionnaires were mailed to participants without internet access with a postage-paid envelope provided for return of questionnaires. Patients again completed all measurement tools at end of treatment, and at 30- and 60-days following end of treatment.

Statistical analysis:

As one measure of feasibility of treatment, adherence to visit schedule was ascertained. We report the number of patients in each group who were able to complete all treatments. Fisher's exact test was performed to assess if adherence is independent of group assignment. For each of the two survey questions used to assess feasibility and acceptability, as described above, a 95% confidence interval for the proportion of participants answering "Yes" was calculated.

Given the small number of patients in the study, exact binomial confidence intervals were calculated since normal distribution could not be assumed.

Descriptive statistics were used to report AEs and SAEs. Incidence and severity were compared between groups.

Effectiveness was based on degree of improvement of pain and compared NRS pain scores in the treatment group and sham group using the Friedman One-Way Repeated Measure Analysis of Variance by Ranks test at baseline, following treatment, and at 30- and 60-day follow-up.

Wilcoxon signed-rank testing was used to determine sustainability over time by comparing scores at baseline to those following treatment, at 30-day follow-up and at 60-day follow-up. A chi-squared analysis comparing the number of treated patients who thought they received treatment versus the number of sham patients who thought they received treatment was performed to determine if masking was effective.

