The target sample size of 22 (11 per arm) was based on previous studies which suggest that the average pain value at baseline is at least 4 on the 0-10 NRS with a standard deviation of the original pain value expected to fall in the range of 1-1.5 in this patient population. A conservative estimate of the standard deviation of the change across patients from Day 1 to Day 10 was approximately up to 2. With 11 patients in each arm and under these assumptions, we were able to detect a change of 2.5 points in the Scrambler group at 80% power, with a difference in proportions of 60% between the two groups.

To explore the impact on co-occurring symptoms when intervening on pain, scores were tabulated for each of the following based on measurement tool data: anxiety, depression, sleep

disturbance and pain interference. Friedman One-Way Repeated Measure Analysis of Variance by Ranks was tabulated for each symptom, comparing the change at baseline, following treatment, and at 30- and 60-day follow-up timepoints in each arm. A subanalysis was similarly conducted in those patients who “responded” to Scrambler treatment versus sham. Based on a cohort of adult patients with spinal cord injury who reported clinically meaningful change in pain over time, “response” was defined as patients with a decrease in NRS pain scores of 1.80 points between baseline and end of treatment.

Demographic and clinical characteristics were compared between Scrambler and sham groups using Mann-Whitney *U* and Chi-squared testing, as appropriate.

Data availability:

Public Law 110-85 (also known as the FDA Amendments Act of 2007) mandates registration and results reporting of "applicable clinical trials" in ClinicalTrials.gov. We support efforts to promote data sharing toward the advancement of science and registered this clinical trial, providing trial design, eligibility criteria and outcomes measures.

Classification of evidence:

This study provides Class II evidence of Scrambler therapy use in patients diagnosed with NMOSD who have central neuropathic pain.

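### The exploratory symptom analysis specifies only within-arm tests, so it cannot estimate Scrambler's effect on symptoms, and a contrast read from its pain-responder subanalysis would not be protected by randomization

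*Combined protocol and SAP*

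**What the plan says.** The symptom objective appears twice, with two different aims.

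- Study objectives and measures: "Although not powered appropriately, an exploratory objective aimed to assess the relationship between improved pain and other co-occurring symptoms". This is an association, and it is declared underpowered.
- Statistical analysis: "To explore the impact on co-occurring symptoms when intervening on pain". This is worded as an effect of treating pain.

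The method is a Friedman test for each of four symptoms, "comparing the change at baseline, following treatment, and at 30- and 60-day follow-up timepoints in each arm". The responder step follows: "A subanalysis was similarly conducted in those patients who “responded” to Scrambler treatment versus sham". Response "was defined as patients with a decrease in NRS pain scores of 1.80 points between baseline and end of treatment".

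The data for a fuller analysis exist: "Patients again completed all measurement tools at end of treatment, and at 30- and 60-days following end of treatment".

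**The concern.** Two features of the text matter.

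1. The Friedman test compares repeated measurements within one set of patients. It has no between-group term. Run separately in each arm, it says whether scores moved over time in that arm, not whether they moved more on Scrambler than on sham. The subanalysis repeats the same procedure in a smaller group.
2. Response is measured after randomization, on the outcome that treatment is meant to change. The sentence does not say whether the group is responders in both arms or Scrambler responders set beside all sham patients. In neither case are the groups the randomized ones.

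At stake is whether the trial can say anything about Scrambler's effect on anxiety, depression, sleep or pain interference. The trial is meant to inform a larger Phase III study, so a symptom signal could carry forward. The primary outcomes (feasibility and acceptability) and the secondary outcomes (safety and NRS pain) are not touched.

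**Working it through.** **1. Which tests are named.** The Statistical analysis section names group comparisons for adherence (Fisher), masking (chi-squared), adverse events (descriptive), NRS pain, and demographic and clinical characteristics (Mann-Whitney U, chi-squared). For symptoms it names only the Friedman test in each arm.

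**2. The plan's own figure.** No figure is given for symptoms. The only one nearby is for pain: "we were able to detect a change of 2.5 points in the Scrambler group at 80% power". With 11 per arm, SD of change 2 and two-sided alpha 0.05 (assumed; the document states neither alpha nor sidedness), a two-sample t-test for a difference of 2.5 has noncentrality 2.5 / (2 × √(2/11)) = 2.93 on 20 df, and power 0.796. That reproduces 80%. A paired test of a 2.5-point change in one arm would have power 0.961. The figure therefore fits a between-arm difference, while the wording is a change in the Scrambler group. Both readings are carried below.

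**3. Who responds.** Take pain change as normal with SD 2 and cut at 1.80. The sham mean drop is not in the documents and is assumed to be 0 to 1.5. With c = (1.80 − mean)/2, P(response) = 1 − Φ(c), and the mean standardized pain change among responders is E = φ(c)/P.

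| Group | Mean drop | c | P | Expected of 11 | E |
|---|---|---|---|---|---|
| Scrambler | 2.5 | −0.35 | 0.637 | 7.0 | 0.589 |
| Sham | 0 | 0.90 | 0.184 | 2.0 | 1.446 |
| Sham | 0.5 | 0.65 | 0.258 | 2.8 | 1.253 |
| Sham | 1.0 | 0.40 | 0.345 | 3.8 | 1.069 |
| Sham | 1.5 | 0.15 | 0.440 | 4.8 | 0.896 |

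**4. Selection bias, if a contrast is read.** Assume no treatment effect on the symptom and a within-arm correlation of 0.5 between symptom change and pain change (not in the documents). Results are in SDs of symptom change.

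- Responders in both arms: 0.5 × (E sham − E Scrambler). At zero sham drop, 0.5 × (1.446 − 0.589) = 0.43. At a drop of 1.5, 0.5 × (0.896 − 0.589) = 0.15. Both favour sham.
- Scrambler responders against all sham: 0.5 × 0.589 = 0.29, in favour of Scrambler.
- All randomized patients: 0.

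Sensitivity:

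- If 2.5 is the between-arm difference, the ranges are 0.32 to 0.43 (both arms) and 0.13 to 0.29 (against all sham).
- With zero sham drop and a Scrambler change of 2.5, correlations of 0.3 and 0.7 give 0.26 and 0.60 (both arms), and 0.18 and 0.41 (against all sham).
- At zero correlation every bias is zero.

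**5. Scale against noise.** In simulated trials of 11 per arm (Scrambler change 2.5, correlation 0.5), the both-arm responder contrast has a sampling SD of 0.77 at zero sham drop and 0.58 at a drop of 1.5. This counts only trials with at least one responder in each arm. At zero sham drop, (1 − 0.184)^11 = 11% of trials have no sham responder, and the contrast does not exist. The unadjusted all-randomized contrast has a sampling SD of √(2/11) = 0.43.

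**6. Separate p-values.** Let true improvement be equal in both groups and present at all three post-baseline visits.

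*Full arms, 11 each* (within-patient correlation 0.5, chi-square p-values): exactly one arm is significant 38%, 50% and 34% of the time at shifts of 0.5, 0.75 and 1.0 per-visit SD.

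*Responder groups* (independent errors, exact critical values). The table gives the chance that only the Scrambler group is significant, which is power(7) × (1 − power(sham n)).

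| Shift, per-visit error SD | 7 v 7 | 7 v 5 | 7 v 2 |
|---|---|---|---|
| 0.5 | 8% | 8% | 9% |
| 1 | 20% | 22% | 25% |
| 1.5 | 25% | 35% | 51% |
| 2 | 15% | 32% | 73% |

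For example, at 2 SD: 0.822 × (1 − 0.116) = 0.727. These units differ from step 4: with independent errors, 2 error SDs equal 2/√2 = 1.41 SDs of change. The documents do not say whether exact or asymptotic p-values are used. With chi-square p-values, two patients cannot reach 0.05 (smallest p 0.11), and 73% becomes about 82%.

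**The case against.** **The plan computes no responder contrast between arms.** If the subanalysis is done in the same way as the full-arm test, it consists of Friedman tests within groups and no Scrambler-minus-sham difference. This stands. A reader might infer that the plan commits to a biased between-arm comparison of responders. The text does not support that: the mention of sham leaves the comparison open but names no test for it. The biases in step 4 apply only if someone adds that contrast.

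**Grouping by response suits the associational aim.** Looking at symptoms in patients whose pain improved addresses the relationship stated under Study objectives and measures. This also stands. A reader might infer that the responder analysis is invalid in itself; it is not, provided that no arm effect is drawn from it. The plan sets no such limit, and its Statistical analysis section states the aim as an effect.

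**The objective is exploratory and declared underpowered.** This lowers the severity. It does not answer the point, because low power concerns imprecision, whereas a missing between-arm comparison and selection after randomization concern what is being estimated.

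**The sizes rest on assumptions, and the largest are extreme.** This stands. Sham change, correlation and symptom shift are not in the documents. The both-arm bias at correlation 0.5 is smaller than its own sampling SD. The 73% needs both a 2 SD shift and exactly two sham responders, and at 0.5 SD group size makes almost no difference.

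**Conclusion.** The point holds in a limited form. As written, the symptom analysis cannot estimate what Scrambler does to symptoms, because no between-arm comparison is specified and separate within-arm p-values cannot stand in for one. That part follows from the text and needs no assumption.

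The selection part is conditional. A Scrambler-versus-sham contrast read from the responder groups would be off by 0.15 to 0.43 SD of symptom change in one direction, or 0.29 SD in the other, depending on how an ambiguous sentence is read. These sizes assume normal pain change with SD 2, a Scrambler change of 2.5, sham drops of 0 to 1.5, correlation 0.5 and no true symptom effect.

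A reader might also infer that the sham responder group would be too small to use. At SD 2, two or fewer sham responders is more likely than not only at the lowest assumed sham drop: 67% at zero, against 43%, 21% and 7% at 0.5, 1.0 and 1.5.

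Nothing here bears on the feasibility, acceptability, safety or pain results. Severity is low.

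**What to change.** 1. For each symptom, estimate the between-arm difference in change in all randomized patients, adjusted for baseline, with a 95% CI. Make end of treatment the main timepoint and add 30 and 60 days. Report all 4 × 3 = 12 estimates as exploratory.
2. For the relationship question, regress symptom change on continuous pain change, both from baseline to end of treatment, in all 22 patients with arm as a covariate (or use a partial Spearman correlation). Give a CI and label the result associational.
3. If responder results are kept, state which patients they include and present them descriptively, with counts and no arm comparison.

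**Cost.** No new data are needed, since the instruments were completed at all four timepoints. The document is written in the past tense, so this means a minor re-analysis as well as rewording. The responder subanalysis loses any inferential role.

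**Precision stays poor.** The 95% CI half-width for item 1 is about 2.093 × √(2/11) = 0.89 residual SD. For item 2, a partial correlation of 0.5 has a Fisher-z standard error of 1/√18 and a CI of about 0.09 to 0.77.
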